### **3.3. Cardiac Amyloidosis Imaging**

#### **3.3.1. Zr-GSK2398852 PET Imaging**

PET allows an accurate assessment of radioactivity distribution in the body after the administration of the radioactivity tracer.

Each PET sequence is anticipated to last 60-90 minutes and will have up to 3 scans per dosing session. All PET scans are expected to be performed within 5 days of Zr-GSK2398852 administration.

From the time of tracer administration multiple blood samples are taken for the measurement of radioactivity concentration in whole blood and plasma. These data will be used in relation to the tissue uptake.

The images can be visually inspected but more important is that selected areas in the images will be used for quantitative evaluation of radioactivity concentration and further used for the modelling.

### **3.3.2. Additional PET Imaging Procedures**

Whenever possible, the following baseline PET procedures should be performed after a subject has passed other eligibility requirements.

#### **3.3.2.1. PiB PET Imaging: Cardiac Amyloid Burden**

The PET tracer Carbon-11 PiB has been used extensively for the characterization of amyloid load in patients with Alzheimer's disease but also in a number of publications for amyloid burden in the heart [[Pilebro 2016](#), [Antoni 2013](#)]. This type of study has shown excellent visualization and quantitative values which identifies amyloid-loaded hearts as compared to hearts without amyloid. The studies have also identified differences in the anatomical location of the amyloid deposits, information which can be of great importance for the interpretation of the Zr-GSK2398852 distribution in the heart.

If logistically possible, this PiB PET procedure will be introduced at a time point which is suitable in relation to technical aspects such as availability of cyclotron and radiochemistry or logistical aspects related to patient handling. It includes a single IV bolus administration of the tracer followed by about 30 minutes scanning over the heart.

#### **3.3.2.2. O-labelled Water PET Imaging: Myocardial Blood Flow**

Oxygen-labelled water (WAT) has been used extensively in PET studies for the characterization and quantitative evaluation of regional tissue blood flow [[Antoni 2013](#), [Dorbala 2014](#)]. Such or similar studies have demonstrated marked and regionally different reductions in the blood flow in the heart of patients with systemic amyloidosis. This is additional information which can be important for the interpretation of the signal in the Zr-GSK2398852 study.

This PET procedure may be introduced at up to two time points which are suitable in relation to technical aspects such as availability of cyclotron and radiochemistry or logistical aspects related the patient handling.

The procedure includes the bolus administration of WAT followed by scanning across the heart for a few minutes.

### 3.3.3. Cardiac Magnetic Resonance (CMR) Imaging

CMR methods precisely and specifically quantify the left ventricle (LV) mass and the cardiac ECV, both of which are increased by the presence and extent of cardiac amyloid deposition. Raised ECV values have been shown to be associated with a worse clinical prognosis in ATTR-CM [[Martinez-Naharro 2017](#)].

However, the specificity of ECV as a measure of amyloid involvement in myocardial tissue remains to be determined. In this study, contrast-enhanced CMR will be used to determine the amyloid load and myocardial perfusion in ATTR-CM patients at baseline. Baseline CMR will also enable exploratory investigations to co-localise regions of Zr-GSK2398852 cardiac uptake on PET imaging with anatomical sites of TTR amyloid deposition within the myocardium, as well as potentially loco-regional intramyocardial perfusion parameters since myocardial blood flow is expected to be an important determinant of Zr-GSK2398852 myocardial uptake and distribution.

Whenever possible, the baseline contrast-enhanced CMR should be performed after a subject has passed other eligibility requirements.

### 3.4. Benefit/Risk Assessment

More detailed information about the known and expected benefits and risks and reasonably expected adverse events of Anti-SAP treatment may be found in the Investigator's Brochure.

Summaries of the pre-clinical and clinical studies conducted with CPHPC alone and with CPHPC + anti-SAP mAb are presented in the Investigator's Brochure [[GlaxoSmithKline Document Number 2012N141587\\_06](#)].

#### 3.4.1. Risk Assessment for Anti-SAP mAb

Given that the administered dose of Zr-GSK2398852 per anti-SAP dosing session will be low (10 mg), the principal risks associated with anti-SAP mAb in this PET study are likely to be associated with the administration of unlabelled anti-SAP mAb.

At this time, there are two main identified risks for administration of unlabelled anti-SAP mAb in this PET study, based on observations in the FIH study: **i)** skin rash (Section [3.4.1.1](#)); **ii)** anti-SAP mAb infusion-related reactions (IRR).

##### 3.4.1.1. Rashes

Many subjects who received 582 mg or more of anti-SAP mAb in the FIH study (SAP115570) developed variable, polymorphic urticarial and/or macular skin rashes with a range of different anatomical distribution, severity and persistence; all but one of these rashes, were self-limiting. Skin biopsy in two other affected AL amyloidosis patients demonstrated pathological changes consistent with an early leukocytoclastic vasculitis (LCV).

The pathophysiological mechanism for these rashes is not known to date but, importantly, it was not associated with any systemic symptoms, signs or organ dysfunction, and in particular, there was no evidence of arthritis or systemic vasculitis in the eye, kidneys or elsewhere. The potential mechanisms will be thoroughly investigated in the ongoing Phase 2 study (Study Number 201464).

**GSK will also inform the study site as to the emerging immuno-toxicological / skin pathological findings from the Anti-SAP Phase 2 study since this might assist the evaluation and management of any rashes which are observed during this PET imaging study.**

See Section 3.4.3 for risk mitigation strategy.

#### **3.4.1.2. Potential for mAb Infusion-Related Reactions (IRR)**

Most subjects receiving more than 200 mg of anti-SAP mAb in the FIH study experienced infusion-related reactions varying in type and severity, which included headache; flushing; hot or cold feelings; chest discomfort; chills; facial, orbital and peripheral oedema; nausea; vomiting; diarrhoea; fatigue; tachycardia; pre-syncope. These symptoms were reduced by slowing or temporarily interrupting the infusion and were further mitigated by pre-medication with hydrocortisone and chlorphenamine.

See Section 3.4.3 for risk mitigation strategy.

#### **3.4.1.3. Potential for Cardiotoxicity**

Cardiac amyloidosis (ATTR & AL) patients have been dosed in the FIH study. This was associated with an overall acceptable safety profile.

Since the minimum effective dose for anti-SAP mAb dependent amyloid removal in the heart of ATTR-CM patients has not yet been established, and because there is a known high background incidence of arrhythmias in this patient population, there remains the theoretical potential for engagement of complement and macrophage mechanisms within the myocardium of subjects receiving anti-SAP mAb TMD up to and including  $\leq 500$  mg. Therefore, this yields a potential risk of cardiotoxicity through disturbance of electrophysiology and / or myocardial contractility, or perfusion.

See Section 3.4.3 for risk mitigation strategy.

#### **3.4.2. Radiation exposure**

The study will involve radiation exposure from up to 2 separate administrations of  $^{89}\text{Zr}$  labelled anti-SAP ( $^{89}\text{Zr}$ -GSK2398852) to patients, each associated with 3 low-dose whole-body CT imaging scans, plus potential PET procedures with PiB and WAT.

In oncology  $^{89}\text{Zr}$ -labelled mAb studies, a minimum administration of 37 MBq is regarded as adequate for good image quality. In some studies, this administration has been repeated up to 3 times. Some of the studies have been associated with other PET studies, notably Fludeoxyglucose (FDG). The studies conducted in the United States (US) have

typically been associated with much higher administrated doses such as 185 MBq [[Pendit-Taskar 2014](#), [Ulaner 2016](#)].

The prognosis of ATTR-CM is similar to that of metastatic cancers, in that the life expectancy is less than 4 years from diagnosis, and the older age at presentation for wild-type ATTR (median 75 years), means that the subjects can be exposed to higher levels of radiation without significantly increasing the risk of developing secondary tumors [[Shuryak 2010](#)].

Based on the above information and rationales, the proposed  $^{89}\text{Zr}$ -GSK2398852 dose is approximately 37 MBq for each administration, 2 dosing sessions per subject, with a total of approximately 74 MBq. The mean effective dose for  $^{89}\text{Zr}$ -mAb PET study was reported to be 0.53 mSv/MBq [[Börjesson 2009](#)], hence 37 MBq of  $^{89}\text{Zr}$ -GSK3128349 in this study would provide approximately 19.61 mSv (37 MBq x 0.53 mSv/MBq) of exposure, which together with the low-dose CT scans (0.5 mSv/CT scan x 3 CT scans) yield approximately 21.11 mSv. The single PiB procedure including its CT component is expected to add 1.5 mSv, and the two WAT procedures to add a total of 1 mSv in radiation exposure.

Total radiation dose exposure per subject is therefore expected to be a maximum of up to 44.7 mSv. With some residual radioactivity in the injection syringe and considering radioactive decay till time of injection, we will aim to be below 44 mSv across the study. Reference [Appendix 9](#) for additional information.

### 3.4.3. Risk Assessment

Potential Risk of Clinical Significance	Summary of Data/Rationale for Risk	Mitigation Strategy
Investigational Product (IP) [GSK2398852; anti-SAP mAb]		

Acute onset rash within first 7 days of infusing anti-SAP mAb
	
Many patients who received 582 mg or more of anti-SAP mAb in the FIH study (SAP115570) developed variable polymorphic urticarial and/or macular skin rashes with a range of different anatomical distributions, severity, and persistence, with all but one case being self-resolving and self-limiting.
 
Skin biopsy in one AL amyloidosis patient who had a diffuse maculopapular / urticarial rash after being administered 600 mg anti-SAP mAb on the first treatment session was reported as a LCV. In this biopsy sample, there was no demonstrable deposition of immunoglobulins, complement, immune complexes, or amyloid in the tissues.
 
A second AL amyloidosis patient with improving liver load (after 1st treatment session) had a diffuse rash after receiving 1000 mg anti-SAP mAb on the 2nd treatment session. The dermato-pathological changes on this subject's skin biopsy was consistent with a lymphocytic / leucocytoclastic vasculitis.
	
Administration of TMDs ≤500 mg per dosing session
 
Dermatological (skin) monitoring
 
Prompt clinical dermatology review dependent on the presenting Grade, persistence and overall temporal evolution of the rash (see Section 12.7)
 
Use of topical or systemic anti-inflammatory medications, including but not restricted to corticosteroids and anti-histamines, at the discretion of Investigator, designee, or dermatologist (as necessary)
 
Subjects will be withdrawn from the study after the 1st dosing session if a rash has not completely resolved by the scheduled time of the 2nd dosing session, or if the rash has been designated as >Grade 2 following session 1 (see Section 8.1.7)

Potential Risk of Clinical Significance	Summary of Data/Rationale for Risk	Mitigation Strategy
Post-inflammatory hyperpigmentation (PIH)	
Some FIH study patients who repeatedly experienced acute rashes with repeat anti-SAP mAb dosing <math>\geq 582</math> mg developed variable PIH.
 
PIH is benign but may only resolve completely after weeks or months, especially in darker skinned individuals.
 
Subjects with hereditary cardiac amyloidosis caused by the V122I TTR variant, which is very largely confined to ethnicities originating in Africa, will thus be at greater risk.
	
Anti-SAP mAb TMD <math>\leq 500</math> mg per dosing session to mitigate risk of acute rashes
 
All subjects who develop PIH will be monitored clinically
 
Dermatology review for all PIH occurrences

Infusion Reactions	
Most subjects receiving more than 200 mg of anti-SAP antibody in the FIH study experienced infusion reactions varying in incidence and severity, which included headache; flushing; hot or cold feelings; chest discomfort; chills; facial, orbital and peripheral oedema; nausea; vomiting; diarrhoea; fatigue; tachycardia; pre-syncope.
 
These symptoms were reduced by slowing or temporarily interrupting the infusion and were further mitigated by pre-medication with hydrocortisone and chlorphenamine.
	
Unlabelled anti-SAP mAb will be given as a single infusion slowly over at least 6 hours where the intended mass dose per dosing session will be <math>>200</math> mg range. (i.e. TMD range: <math>200 \text{ mg} < \text{TMD} \leq 500 \text{ mg}</math>)
 
Interrupting the infusion and/or reducing the rate of administration of each mAb infusion
 
Hydrocortisone premedication
 
Antihistamine premedication
 
Careful monitoring of blood pressure, and appropriate clinical management if required (e.g. fluid balance and urine output with immediate access to IV fluids).
 
Use of anti-emetics for nausea & vomiting

Myocarditis	
The intended and desired pharmacodynamics (PD) mechanism by which anti-SAP mAb treatment mediates clearance of amyloid deposits from the extracellular space is absolutely dependent on antibody binding to amyloid
	
Administration of anti-SAP mAb TMD during each session which will be up to approximately 12-fold lower than anti-SAP mAb doses administered to cardiac amyloidosis subjects in the FIH study (SAP115570)

Potential Risk of Clinical Significance	Summary of Data/Rationale for Risk	Mitigation Strategy
	
deposits in the heart, activation of complement and attraction of macrophage infiltration and fusogenic activation to form multinucleate giant cells (MGCs). The clinical experience to date has been reassuring that these processes or the consequent removal of amyloid do not have adverse effects on tissues or organs, including the heart. However it could be speculated that cardiac function could be impaired through disturbance of electrophysiology and/or myocardial contractility or perfusion.
	
(i.e. 80 mg ≤TMD ≤500 mg per dosing session)
 
Comprehensive inpatient cardiac monitoring comprising:
 
Serial heart rate and blood pressure measurement
 
Continuous inpatient telemetry during and after each anti-SAP treatment session
 
Serial 12-lead ECG recording
 
Serial inpatient evaluations of cardiac troponin T and NT-proBNP
 
2D-ECHO will be performed at Screening to provide reference cardiac functional data in the event of cardiac adverse event(s) during the study which might perturb cardiac function.
 
Non-implantable cardiac monitoring devices (e.g. BodyGuardian) will be used to evaluate the background electrophysiology of subjects at Screening. The same monitoring device will be used for at least 7 consecutive days after in-patient discharge to detect potential later-onset cardiac electrophysiology changes associated with administration of an anti-SAP mAb TMD.

Investigational Product (IP) [GSK2315698 - CPHPC]		
Epistaxis	
Small volume nose bleeds have been noted in a few subjects in previous studies. These events have been self-limiting, and not associated with any evidence of thrombocytopenia or coagulopathy.
 
No causal relationship to Anti-SAP treatment has been
	
Serial haemoglobin & platelet monitoring, and Screening coagulation test.
 
These investigations may be repeated if an epistaxis event occurs.

Potential Risk of Clinical Significance	Summary of Data/Rationale for Risk	Mitigation Strategy
	identified at this time.	Serial heart rate and blood pressure measurement
CMR Contrast Agent - gadolinium (Gd)		
Delayed excretion and tissue accumulation of gadolinium contrast after CMR scan	
Gadolinium is mostly excreted in the urine and this is impaired in subjects with reduced renal function. Patients with systemic AL amyloidosis very often have renal amyloid and impaired renal function while cardiac ATTR patients are all elderly and therefore may also have non-amyloid chronic kidney disease. All these individuals are therefore at increased risk of Gd accumulation.
 
FDA have issued an alert for tissue accumulation of Gd in organs including the brain following its repeated use, including some patients with normal renal function, although no new neurological complications have been reported to date
	
Gd-contrast CMR will be only performed once during the study, at Screening
 
Exclusion of patients with eGFR <50 mL/min
 
eGFR will be checked prior to Gd-contrast CMR

Nephrogenic systemic fibrosis (NSF) / dermatopathy (NSD)	A very rare cause of cutaneous and, even more rarely, systemic fibrosis, including in the heart, caused by Gd contrast agents, with typical rash and characteristic histopathology. Possibly related to impaired renal function.	
Exclusion of patients with estimated glomerular filtration rate (eGFR) <50 mL/min (see exclusion criteria)
 
Monitoring of serum creatinine before and after administration of Gd contrast agent.
 
Dermatological inspection for rashes.

Allergic reactions to Gd contrast	Gd contrast agents can cause allergic reactions especially with IV bolus administration	
History before infusion regarding any reactions to previous imaging contrast agents.
 
Slow IV infusion of Gd contrast with ability to stop immediately if subject develops symptoms.

Potential Risk of Clinical Significance	Summary of Data/Rationale for Risk	Mitigation Strategy
Procedural risks		

Subjects exposed to ionising radiation as a consequence of participation in this study (e.g. Zr-GSK2398852 imaging).
	
Ionising radiation exposure from PET scanning comes from the administered radioligand and CT examination. The total radiation burden per subject is calculated as 21.1 mSv per Zr-GSK2398852 scan session; and the single PiB and two WAT scans together 2.5 mSv; up to total 44.7 mSv for all PET scans and this corresponds to a lifetime risk of a fatal malignancy of about 1 in 600 [ICRP 2007].
 
Subjects who participate will receive a radiation exposure up to a maximum of 44.7 mSv across two separate dosing sessions.
 
The ceiling radiation exposure of 44.7 mSv is judged as safe to the individual, and justified on a trial basis due to the clinically severe and life-limiting nature of ATTR cardiomyopathy, and the importance to the study objectives of optimising the signal-noise ratio from the myocardium during each PET scan
	
The study has been designed to keep the radiation dose as low as reasonably practicable (ALARP) whilst obtaining images of sufficient quality to meet the objectives.
 
Subjects <65 years of age will not be eligible
 
The study will exclude women of childbearing potential.
 
Subjects who have been exposed to ionising radiation in excess of 10 mSv above background over the previous three-year period as a result of occupational exposure to radiation or as a result of research studies are excluded. Clinically justified (therapeutic or diagnostic) exposures are not included in the exposure calculation. Subjects are asked about any occupational exposure or previous participation in research studies at screening so that dose estimates can be obtained where necessary.

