### 8.1.3. Renal Function Discontinuation Criteria

Subjects will not receive anti-SAP mAb if

- The eGFR calculated by the MDRD equation has reduced to  $<40$  mL/min/1.73m^2 after Screening,
- or
- There has been a reduction in eGFR from baseline by  $>50\%$ .

If the eGFR falls to between 40 – 50 during the trial, the subject can continue participation at the investigator/designee's discretion.

Dose adjustment of IV and / or SC CPHPC may be necessary for subjects with reduced eGFR at baseline, before administration of anti-SAP mAb in the 2nd dosing session, or at any time during the study; refer to Section 7.2.1 and Table 8 for CPHPC renal dosing regimen.

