#### **9.3.4.3. Imaging for Investigation of Cardiac Adverse Events**

Contrast-enhanced CMR and ECHO methodologies will be detailed in the separate Image Acquisition and Analysis Manual.

A single 2-D Echocardiogram will be performed at baseline for reference, in the event of an adverse cardiac event being detected during the study (e.g. worsening heart failure symptoms or an unexpected large rise in NT-proBNP levels) which in the opinion of the Investigator or designee would require repeat Echocardiogram to re-evaluate cardiac function.

Similarly, repeat CMR(s) can also be performed at any time during the study (to compare against the baseline CMR) to enable a more detailed evaluation of cardiac function.

Furthermore, at the discretion of the investigator / designee in consultation with the Medical Monitor, a repeat CMR can be performed in the unlikely event that there is suspected change in cardiac amyloid load – e.g. in the clinical opinion of the investigator

or designee, an appreciable reduction in NT-proBNP levels from baseline during or after any of the two Anti-SAP dosing sessions.

Wherever feasible, repeat CMR scan(s) should be performed at the local study site preferably using the same MRI scanner and IV contrast agent as that used at Screening.

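### The gadolinium risk table promises a single contrast CMR, but Section 9.3.4.3 allows event-driven repeats with the same agent, and no on-study eGFR value for withholding contrast is stated

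*Protocol*

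**What the plan says.** In the risk table of Protocol Section 3.4.3, the row on delayed excretion and tissue accumulation of gadolinium describes the hazard partly in terms of repetition: "FDA have issued an alert for tissue accumulation of Gd in organs including the brain following its repeated use". It lists three mitigations: "Gd-contrast CMR will be only performed once during the study, at Screening"; exclusion of patients with eGFR below 50 mL/min; and "eGFR will be checked prior to Gd-contrast CMR". The separate row on nephrogenic systemic fibrosis lists the same exclusion, serum creatinine monitoring before and after the contrast agent, and skin inspection.

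Section 9.3.4.3 says that "repeat CMR(s) can also be performed at any time during the study" so that cardiac function can be examined in more detail against the baseline scan. It adds that, at the investigator's or designee's discretion and in consultation with the Medical Monitor, "a repeat CMR can be performed in the unlikely event that there is suspected change in cardiac amyloid load", and gives an appreciable fall in NT-proBNP as an example. Where feasible, repeats are to be done at the local site, "preferably using the same MRI scanner and IV contrast agent as that used at Screening".

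Section 9.6.2 also provides for follow-up CMR when clinically indicated for a possible cardiac adverse event. Section 9.8.1, under Efficacy, asks that any fall in NT-proBNP be read alongside changes in LV mass or ECV on repeat CMR.

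On renal function, exclusion criterion 7 in Section 6.2 sets the eGFR limit of 50 mL/min at Screening. Section 8.1.3 says that if eGFR falls to 40–50 during the trial, "the subject can continue participation at the investigator/designee's discretion".

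**The concern.** The accumulation row names repeated use as part of the hazard, and the once-only statement is the listed control that answers it directly. If another section allows contrast to be repeated, that control does not describe the study as it may be run.

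Two things are at stake. Ethics committees, investigators and subjects take procedural exposure from the risk table. Sections 3.4.4 and 3.4.5 say that participants are not expected to gain direct therapeutic benefit, so that exposure should be stated accurately. A site also receives conflicting instructions: an investigator who repeats a contrast scan under Section 9.3.4.3 departs from the limit in Section 3.4.3.

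**Working it through.** No formula applies. The check sets the sections side by side.

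1. **Number of contrast scans.** Section 3.4.3 gives 1, with no exception. The Schedule of Activities also shows 1 scheduled contrast MRI, at Baseline. Under Section 9.3.4.3 the permitted number is 1 + k, where k is the number of contingent repeats. No upper value for k is stated there or in Section 9.6.2. The two statements agree only if k = 0, and Section 9.3.4.3 exists to allow k > 0.

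2. **Do repeats involve contrast?** Section 9.3.4.3 opens by referring to contrast-enhanced CMR methods, and its preference for repeats names the IV contrast agent used at the first scan. Section 3.3.3 assigns measurement of amyloid load to contrast-enhanced CMR, and a suspected change in amyloid load is one of the repeat triggers. The text therefore foresees contrast at repeats, although it states a preference and not a requirement.

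3. **Are all repeats management of harm?** No. The first trigger is a cardiac adverse event. The second is a suspected change in amyloid load, illustrated by a fall in NT-proBNP, and Section 9.8.1 places the reading of such a fall under Efficacy. That trigger is investigational.

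4. **Which mitigations are affected?** Of the three in the accumulation row, only the once-only statement conflicts with Section 9.3.4.3. The eGFR check is not worded as limited to the first scan. Nor are the creatinine monitoring and skin inspection in the fibrosis row, where the once-only limit does not appear.

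5. **Renal conditions at a repeat.**
   - Entry: eGFR below 50 mL/min is excluded, assessed at Screening.
   - On study: a subject whose eGFR falls to 40–50 may continue at discretion (Section 8.1.3).
   - The firm limits in Section 8.1.3 (eGFR below 40, or a fall of more than 50% from baseline) bar the antibody; the section does not mention contrast.
   - Section 9.3.4.3 contains no renal condition.
   - The eGFR check in Section 3.4.3 gives no value at which contrast is withheld.

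   A subject below the entry limit can therefore be on study when a repeat scan is permitted. Nothing in these sections says whether contrast may then be given.

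**The case against.** The strongest defence is that the risk table describes the scheduled procedure and that event-driven imaging is a separate matter. The Schedule of Activities shows a single CMR. Section 2.2 of the statistical analysis plan calls CMR and echocardiography a baseline safety measurement only. Section 9.6.2 ties follow-up scans to clinical indication. On this reading, one exception clause in the table would cure the problem. It is a fair account of what may have been intended, but the table does not say it: its limit covers the whole study and makes no exception. The amyloid-load trigger also goes beyond adverse-event care.

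Other parts of the defence stand and limit the point. A reader might infer any of the following, and the documents do not support them:

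- **That exposure is unlimited.** Repeats are contingent. The amyloid-load trigger is described as unlikely and requires consultation with the Medical Monitor. The absence of a stated maximum does not amount to permission for unlimited scanning.
- **That the gadolinium mitigation fails as a whole.** The eGFR check, creatinine monitoring, skin inspection and entry exclusion all remain as written.
- **That contrast at eGFR 40–50 is authorised.** Section 8.1.3 concerns the antibody and continued participation. Contrast below the entry limit is an inference from that rule and the silence of Section 9.3.4.3.
- **That Screening in the table against Baseline in the Schedule of Activities is a second contradiction.** Section 9.3.4.3 uses both labels for the same scan. This is loose naming and does not bear on exposure.

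**Conclusion.** The once-only mitigation is contradicted by Section 9.3.4.3 and cannot stand as written. Section 3.4.3 states one contrast CMR; the protocol permits one plus contingent repeats with no stated maximum. The table therefore understates the permitted contingent exposure. How often repeats would occur cannot be estimated from the documents.

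The renal part is a gap in the text: no on-study eGFR value for withholding contrast is given, so contrast at 40–50, below the entry limit of 50, is not ruled out.

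The conclusion assumes that the preference for the same IV contrast agent means that repeats would normally be contrast-enhanced. The renal part also assumes that the silence of Section 9.3.4.3 on eGFR is not filled by a document outside those reviewed, such as the image acquisition manual. Even if it were, the once-only statement would still need correcting. The point is one of internal consistency in a safety statement and has no effect on endpoints, sample size or analysis.

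**What to change.** Reconcile Protocol Sections 3.4.3, 8.1.3, 9.3.4.3 and 9.6.2 so that they agree on:

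- whether repeat contrast CMR is permitted and, if so, on which triggers;
- the renal conditions that apply to a repeat, including for a subject who continues under Section 8.1.3 with eGFR of 40–50;
- whether the eGFR check and creatinine monitoring in the risk table apply to every contrast administration.

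If repeats remain permitted, the once-only entry in the risk table should state the exception; if they do not, Section 9.3.4.3 and the related text in Sections 9.6.2 and 9.8.1 need to change. Which clinical rule is right is for the sponsor to decide. The cost is protocol wording only, with no change to the design, the sample size or the statistical analysis plan.
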